6.4 Monitoring of Safety Endpoints

Monitoring of the following events will occur:

Infections:

- Infection events associated with this study will be done by examination of all cultures (blood, urine, and respiratory) obtained from the time of randomization through Day 7 (168 hours).
- The final results of all cultures sent between the time of randomization and Day 7 will be obtained and recorded in the database.

Arrhythmias:

- All arrhythmias occurring from the time of randomization through Day 7 will be recorded.

Blood Products:

- In addition, blood products received from the time of randomization through Day 7 will be recorded.
- Blood products are defined specifically here to include red blood cells, platelets, fresh frozen plasma, and cryoprecipitate.
- In addition to blood products received, surgeries to treat bleeding will also be recorded from randomization through Day 7.

Mortality:

- Mortality will be recorded at 28 days post randomization for all enrolled patients.

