4.4 Safety Endpoints

Safety endpoints of this study are:

1. All-cause 28 day mortality;

2. Incidence of culture proven infection (blood, urine, respiratory, or other) within 7 days of cardiac arrest;
3. Incidence of arrhythmias within 7 days of cardiac arrest;
4. Blood products required within 7 days of cardiac arrest. Blood products are defined specifically here to include red blood cells, platelets, fresh frozen plasma, and cryoprecipitate.

5 Patient Eligibility and Accrual

The study population is the pediatric population greater than 48 hours and less than 18 years of age who experience cardiac arrest for two minutes or longer with return of spontaneous circulation (ROSC/ROC).

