- any condition in which direct skin surface cooling would be contraindicated, such as large burns, decubitus ulcers, cellulitis, or other conditions with disrupted skin integrity (NOTE: patients with open chest CPR should be included but placement of cooling mattresses will be modified as needed); OR
- previous enrollment in the THAPCA Trials.

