Blood cultures will be obtained at the time of randomization and on days 1, 2, and 3. Days are defined as 24 hour periods from 12:00 a.m. to 11:59 p.m. Day 1 is the first full 24 hour period after randomization. Urine cultures will be obtained at the time of randomization and on days 2 and 4. The final results of all cultures sent within 7 days of enrollment will be obtained and recorded in the database.

Chest x-rays will be done daily during the intervention period in order to confirm temperature probe position. If multiple radiographic examinations are obtained during any study day, the examination closest to 8:00 A.M. will be recorded.

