8.4 Post Intervention Through Discharge

After the intervention period, patients will be monitored according to standard PICU clinical practice for the participating site. Patients will be reviewed daily for their minimum and maximum temperatures through day 10 or hospital discharge, whichever is earlier. The results of all blood, urine and respiratory cultures conducted up to seven days after cardiac arrest will be recorded. Concomitant medications will be recorded from the time of randomization through day 7. Select procedures and therapies will be recorded through hospital discharge. Blood products received within seven days of arrest will be recorded. Adverse events will be recorded from the time of randomization through Day 14. Adverse events that have not resolved by Day 14 will be followed until resolution or hospital discharge, whichever is earlier. If the Adverse Event has not resolved at the time of hospital discharge, the Research Team should follow the guidelines for AE follow-up outlined

in section 11.2.6 of the protocol. PICU and hospital discharge information will be captured.

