Excessive cooling below the therapeutic range. This complication will be treated by increasing the Blanketrol III temperature so that the patient warms to the therapeutic range (32 to 34°C). Excessive cooling below the therapeutic range in the THAPCA Trials could result in life-threatening cardiac arrhythmias. If cooling below the therapeutic range occurs in patients randomized to receive hypothermia, the patient will be rewarmed to the therapeutic range of 32 to 34°C immediately. Arrhythmias will be managed according to standard AHA PALS guidelines. Excessive cooling will be avoided by utilizing two central temperature probes (esophageal and bladder or rectal) and monitoring subject temperature on a continual basis. The temperature of the water in the Blanketrol III will also be monitored and recorded, and temperature control in all subjects will use the servo-control mechanism available with the Blanketrol III. The patient will not be cooled below 32-34 °C therapeutic range. The study investigator will be contacted for central temperatures of 31.0 °C or less. In the event that the temperature difference between central measures is greater than 1.0 °C, the study investigator will be also be notified.

Cardiac arrhythmias. Serious cardiac arrhythmias are not expected to occur unless the temperature falls well below 30 °C. If a clinically significant arrhythmia develops and persists, then the patient would be rewarmed to normal range if determined by the clinical care team to be necessary.

Infection. Infection rates are expected to be high in both groups of subjects (normothermia and hypothermia groups), based on our prior cohort study data of cardiac arrest patients. The clinical team will utilize antibiotics per their usual clinical site practice in the post arrest population. The THAPCA Trials will monitor both hypothermia and normothermia (control) groups for blood stream and urinary infections as outlined in Section 6.3 of the protocol. In the event of a positive culture or suspicion of possible infection, appropriate antibiotics will be initiated based on the clinical care team's hospital experience.

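### The infection safety endpoint counts positive cultures from any site, but Section 6.4's event rule and Sections 8.3 and 8.4 name only blood, urine and respiratory cultures

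*Protocol*

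**What the plan says.** The endpoint is defined in Section 4.4 as "Incidence of culture proven infection (blood, urine, respiratory, or other) within 7 days of cardiac arrest". Sections 1.2.4 and 9.4 use the same definition. Section 9.4 compares it between arms by chi-square test in each trial separately, with rate ratios and 95% confidence intervals.

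Section 6.4, which describes how the safety endpoints are monitored, says: "Infection events associated with this study will be done by examination of all cultures (blood, urine, and respiratory) obtained from the time of randomization through", with the window closing on the seventh day. Its next bullet says: "The final results of all cultures sent between the time of randomization and Day 7 will be obtained and recorded in the database". Section 6.3 has a similar sentence: "The final results of all cultures sent within 7 days of enrollment will be obtained and recorded in the database".

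The data-collection summary is narrower. Section 8.4 says: "The results of all blood, urine and respiratory cultures conducted up to seven days after cardiac arrest will be recorded". Section 8.3 names the same three culture types for the intervention period. Section 10.4.2 says that the trials "will monitor both hypothermia and normothermia (control) groups for blood stream and urinary infections", with a reference back to Section 6.3.

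**The concern.** Three definitions of the endpoint include an open category, and three operational statements leave it out. A reader of the first infection bullet of 6.4 would not look at a wound, mediastinal or skin culture when identifying infection events. A coordinator working from 8.3 and 8.4 might not enter one.

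Infection is a harm the protocol itself links to cooling. Section 2.3.3 lists it among the potential adverse effects, and Section 2.2.2 notes a trend towards more infection in one of the adult trials. The omitted category is not remote in this population: under Section 5.2 "patients with open chest CPR should be included but placement of cooling mattresses will be modified as needed", and Section 10.4.2 foresees possible skin injury from the cooling blanket. If the narrower rule is applied, a formally tested safety endpoint is reported on fewer culture sites than its definition states.

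**Working it through.** There is no figure in the plan to reproduce and no sample size, power or error rate is involved. The check sets the statements side by side.

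| Protocol section | Function | Culture sites covered |
|---|---|---|
| 1.2.4, 4.4, 9.4 | Endpoint definition and analysis | Blood, urine, respiratory, other |
| 6.4, first infection bullet | Finding infection events | Blood, urine, respiratory |
| 6.4, second infection bullet | Recording in the database | All, no limit stated |
| 6.3 | Recording in the database | All, no limit stated |
| 8.3, 8.4 | Recording (summary) | Blood, urine, respiratory |
| 10.4.2 | Risk text, refers to 6.3 | Bloodstream, urinary |
| 11.2.3, 11.2.4 | Adverse event and serious adverse event reporting | No limit stated |

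**Step 1: finding versus recording.** The two infection bullets of 6.4 do different jobs. The second puts results in the database; the first says which cultures are examined to identify an event. Under both together, a wound isolate can be in the database and still not be an endpoint event. The second bullet could also be read as referring to the three types just listed.

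**Step 2: recording versus recording.** Sections 6.3 and 8.4 both describe which culture results are recorded, and they differ on site. A centre that follows 6.3 enters an other-site culture; a centre that follows 8.4 need not.

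**Step 3: who is affected.** The endpoint is binary for each child. Write B, U, R and O for at least one positive culture from blood, urine, respiratory and other sites.

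- Broad rule: event if B or U or R or O.
- Narrow rule: event if B or U or R.
- Difference: children with O and none of B, U, R.

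A child with a positive wound culture and a positive blood culture is an event under both rules. Only the child whose sole positive culture is from another site changes status.

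**Step 4: effect on the comparison.** Let d be the true difference in incidence between arms under the broad rule, and let q_H and q_N be the proportions of children in the hypothermia and normothermia arms with other-site cultures only. Under the narrow rule the difference becomes d − (q_H − q_N). If q_H = q_N, the difference is unchanged and both incidences are understated by the same amount. If cooling raises other-site infection in particular, that part of the excess drops out. The protocol gives neither q_H nor q_N, so no number can be put in.

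**Step 5: effect of uneven reading across centres.** Randomization is stratified by centre (Section 6.1), so a centre's choice of rule, if applied alike to its patients, falls on both arms. The likely result is an inconsistent count rather than a bias towards one arm. The clinical team is not blinded (Section 6), however, so an explicit rule is safer than one left to local reading.

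**The case against.** The strongest reply is that other-site infections are not lost. Section 6.3 and the second infection bullet of 6.4 require all culture results through the 7-day window, with no site limit. Section 9.4 analyses the broad definition, so the endpoint could be derived as defined from those data. Section 8 introduces itself as a summary, and a shorter list there need not override 6.3. Section 10.4.2 points to the blood and urine cultures scheduled in 6.3 and does not define the endpoint. Adverse events are recorded whatever the site (11.2.3), serious culture-positive infections need notification within 24 hours (11.2.4), and the DSMB reviews all adverse events (11.2.5).

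Most of this stands. A reader might infer from the first infection bullet of 6.4 that wound and chest infections are necessarily missed, or that an excess confined to such sites would go unreported. The protocol does not support either inference, for the reasons just given. Section 10.4.2 is also weak evidence of a contradiction.

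What the reply does not remove is the disagreement itself. The text that says how infection events are found leaves out a category in the definition, and nothing states which text governs. The adverse event sections are not said to feed safety endpoint 2, so an infection reported there need not enter the chi-square comparison.

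**Conclusion.** The contradiction is real and limited. The protocol disagrees with itself on whether a positive culture from a site other than blood, urine or the respiratory tract is collected and counted for safety endpoint 2. Such an infection may be missed or counted unevenly across centres; it is not shown that it would be.

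The effect is confined to children whose only positive culture is from another site. Its size cannot be derived, since the protocol gives no infection rate by site, and the share of infections at other sites would not in any case equal the share of children misclassified. The conclusion assumes that the definition given three times is the intended one. The primary endpoint is untouched. The point is worth correcting because the endpoint is formally tested, infection is a named risk of cooling, and the correction is nearly free.

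**What to change.** Reconcile the passages with the endpoint definition. In the first infection bullet of Section 6.4, and in Sections 8.3 and 8.4, change the list of cultures to: all cultures (blood, urine, respiratory, or other). This adopts the definition in 1.2.4, 4.4 and 9.4 and the recording that 6.3 already requires.

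It is best settled before data are collected, because cultures that a centre did not enter would later have to be recovered from charts.

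The cost is wording in three sections. It calls for no new cultures or staff and no change in patient care. Reporting incidence by culture site, and adjusting the sentence in 10.4.2, are optional.

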5.7 Long Term Follow-up

Children who were enrolled in the THAPCA Trials represent a very valuable group to study for long term cognitive, developmental and medical sequelae. The subjects legal representative will be approached for consent to be contacted for future studies when deemed appropriate by the clinical centers IRB (i.e. at time of THAPCA consent, between 3 and 12 month visits or after the 12 month visit as appropriate).

6 Study Design & Methods

The THAPCA Trials are two prospective randomized controlled trials of therapeutic hypothermia after cardiac arrest in children. Each THAPCA Trial will be analyzed as an intention to treat study. The THAPCA Trials include one for out-of-hospital cardiac arrests (THAPCA-OH Trial), and one for in-hospital cardiac arrests (THAPCA-IH Trial) (see Figure 2). These trials will be analyzed separately, because etiologies and patient outcomes of these groups are substantially different (see Section 2.3.2 on page 18).

[figure not shown]

Figure 2: THAPCA Trials Diagram

The clinical care team (composed of physicians, nurses, and others) involved with direct patient care and the patient’s family will not be blinded to the treatment group, because temperature is a routine vital sign required for patient care. However, individuals who conduct assessment of neurobehavioral outcome status at three and 12 months following CA will be blinded to the treatment group assignment.

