Once the patient has achieved the goal temperature (32 to 34 °C), the mattress placed on top of the patient may be moved, however, the mattress

underneath the patient will be left in place. Nursing staff will adjust the Blanketrol III unit as needed to maintain a temperature in the goal range. The hypothermia group will then be maintained in the goal temperature range for 48 hours. Rewarming will then occur over approximately 16 hours (0.7 °C every 4 hours) to normothermia (36.0 °C), which should occur at approximately 72 hours after intervention begins. Temperature will again be recorded every 30 minutes during the rewarming period.

From 72 hours or end of rewarming until 120 hours (end of day 5), the hypothermia group will be maintained in the normothermic range (36-37.5 °C) using the Blanketrol III, and temperature will be recorded every four hours. After 120 hours, temperature management will be according to the normal practice of the clinical care team.

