9.4 Safety Analyses

Safety endpoints of this study are:

1. All-cause 28 day mortality;
2. Incidence of culture proven infection (blood, urine, respiratory, or other) within 7 days of cardiac arrest;
3. Incidence of arrhythmias within 7 days of cardiac arrest;
4. Blood products required within 7 days of cardiac arrest. Blood products are defined specifically here to include red blood cells, platelets, fresh frozen plasma, and cryoprecipitate.

Differences between the two study arms with respect to these binary outcomes will be evaluated using a separate chi-square test for each of the THAPCA Trials. Appropriate exact tests will be employed in the case of excessively small expected cell sizes. Rate ratios and 95% confidence intervals will also be described. A secondary analysis will employ the Mantel-Haenszel test to quantify the treatment effect adjusted by center, and the Breslow-Day test (which we recognize will have limited power, as the number of subjects within most centers will be quite low) will be used to assess if there is evidence that treatment effect varies across center.

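### The 7-day infection endpoint pools scheduled with clinician-ordered cultures, so a difference between arms in how often cultures are sent cannot be told apart from a difference in infection

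*Protocol*

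**What the plan says.** The endpoint in section 9.4 is "Incidence of culture proven infection (blood, urine, respiratory, or other) within 7 days of cardiac arrest". Section 6.4 says that infection events are found by "examination of all cultures (blood, urine, and respiratory) obtained from the time of randomization through Day 7 (168 hours", and section 6.3 that "The final results of all cultures sent within 7 days of enrollment will be obtained and recorded in the database". A culture ordered for clinical reasons therefore counts in the same way as a scheduled one.

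The schedule in section 6.3 is the same in both arms: "Blood cultures will be obtained at the time of randomization and on days 1, 2, and 3", and "Urine cultures will be obtained at the time of randomization and on days 2 and 4". No respiratory or other culture is scheduled. Section 10.4.2 agrees, saying that the trials will monitor both "groups for blood stream and urinary infections as outlined in Section 6.3 of the protocol".

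Section 6 states that the clinical team "will not be blinded to the treatment group, because temperature is a routine vital sign required for patient care".

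On temperature, section 7.1 says that "The hypothermia group will then be maintained in the goal temperature range for 48 hours", followed by about 16 hours of rewarming that ends at roughly 72 hours. The normothermic range then applies until 120 hours. Section 7.2 holds controls at 36.0 to 37.5 °C through 120 hours and foresees temperatures above 38.0 °C despite acetaminophen and device cooling.

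Section 9.4 fixes a chi-square test on the binary outcome, a rate ratio with its interval, and a center-adjusted Mantel-Haenszel analysis. None of these separates scheduled from clinician-ordered cultures.

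**The concern.** A culture-proven infection is counted only if somebody sends a culture. For the scheduled samples that chance is set by the protocol and is equal by arm. For the rest it depends on the judgement of staff who know the arm and who see different signs in the two arms.

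Two forces pull in opposite directions. A child at 32-34 °C cannot show fever, so one common prompt for a culture is absent there but only blunted in controls. On the other hand, section 2.3.3 names infection as a possible adverse effect of cooling and section 2.2.2 mentions an infection trend in the European adult trial, so staff may culture cooled children more readily.

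Infection is one of four safety endpoints. Less culturing under cooling could hide a real excess, and more could create a false one. The pooled test cannot tell which has happened. Adjusting for center does not help, because the difference would lie between arms within a center.

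**Working it through.** **No plan figure to reproduce.** The protocol gives no infection rate, detectable difference or power for this endpoint. Section 10.4.2 says only that rates are expected to be high.

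**Step 1: share of the window in which fever cannot show or is altered by rewarming.** Inputs are 1 to 4 h to target, 48 h maintenance, about 16 h rewarming and an end of rewarming at about 72 h (section 7.1), and a window of 168 h (section 6.4).
- Maintenance and rewarming: (48 + 16)/168 = 64/168 = 38.1%.
- With 4 h induction: 68/168 = 40.5%.
- The protocol's own approximate 72 h: 72/168 = 42.9%.
- Temperature control to 120 h, in **both** arms: 120/168 = 71.4%.

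**Step 2: which cultures are exposed.** Section 6.3 defines day 1 as the first full calendar day after randomization, so it starts s hours after randomization, with s between 0 and 24. Days 1 to 3 then run from s to s + 72 hours and lie largely within cooling and rewarming. Day 4 starts at s + 72 hours, at or after the end of rewarming.

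| Culture | Scheduled after randomization | Could frequency differ by arm? |
|---|---|---|
| Blood | Days 1, 2, 3 | Only for off-schedule samples, including all after day 3 |
| Urine | Days 2, 4 | Only for off-schedule samples |
| Respiratory | None | Yes |
| Other | None | Yes |

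**Step 3: what a difference in culturing would do.** This is an illustration with assumed values. Let u be the share of infections that only a clinician-ordered culture in the cooled period would find. Let m_H and m_C be the shares of those missed in the hypothermia and control arms. Then

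observed RR = true RR × (1 − u·m_H)/(1 − u·m_C).

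With no true effect (true RR = 1) and u from 0.1 to 0.4:

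| m_H | m_C | u = 0.1 | u = 0.4 |
|---|---|---|---|
| 0.30 | 0 | 0.97/1 = 0.97 | 0.88/1 = 0.88 |
| 0.30 | 0.15 | 0.97/0.985 = 0.985 | 0.88/0.94 = 0.94 |
| 0.30 | 0.30 | 1.00 | 1.00 |
| 0 | 0.30 | 1/0.97 = 1.03 | 1/0.88 = 1.14 |

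The last row is the opposite case, in which staff culture cooled children more. No value of u, m_H or m_C can be taken from the protocol.

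**Step 4: the restricted comparison.** If only scheduled blood and urine cultures are counted, the protocol fixes when they are sent. Then m_H = m_C and the factor is 1.00 for those two sites. It says nothing about respiratory or other infection.

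**The case against.** The strongest case against runs as follows.

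- **Both arms are temperature-controlled.** Controls are held at or below 37.5 °C by the same device for 120 hours. This stands. The contrast is fever abolished against fever blunted, for part of the window.
- **No section makes fever a trigger for culture.** Section 7.2 responds to high temperature with acetaminophen, device cooling and vecuronium, and section 10.4.2 speaks only of suspected infection. This stands too. Fever as a prompt is a reasonable assumption about practice, not a protocol rule.
- **Other safeguards exist.** The scheduled blood cultures fall largely in the cooled period. Both arms also have a daily blood count (section 6.3) and a daily chest x-ray, which section 8.3 says is used to look for new infiltrates. These narrow the problem. They do not make clinician-ordered cultures equal by arm, and section 2.3.3 lists neutropenia as a possible effect of cooling, so the white count may not be neutral either.
- **Delay is not loss.** An infection cultured after rewarming but by Day 7 still counts, and about 168 − 72 = 96 hours remain. This stands.
- **The restricted comparison drops the most exposed sources.** This is correct, so respiratory and other infections have to be shown beside it.
- **A breakdown of a safety endpoint can be left to the analysis plan.** This is partly right, and a plan not seen here may contain one. But the protocol itself fixes the endpoint, the ascertainment and the test, and whether a culture was scheduled is best recorded as it is sent.

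A reader might infer something stronger: that cooling removes fever as a trigger in one arm only, so that roughly 10 to 21% of cooled-arm infections go unseen (0.38 × 0.5 × 0.5 = 9.5%; 0.38 × 0.7 × 0.8 = 21%). The documents do not support this. The shares found only by unscheduled cultures (50 to 70%) and triggered by fever (50 to 80%) are assumed. The product also takes no loss in controls, treats every delayed culture as lost, and allows for one direction only.

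**Conclusion.** The pooled infection endpoint mixes cultures whose frequency the protocol fixes equally in both arms with cultures whose frequency unblinded staff decide. The stated analysis cannot separate a difference in culturing from a difference in infection. The exposed part is mainly respiratory, other and off-schedule cultures. The period in which the fever signal differs most is about 64 to 72 of 168 hours (38 to 43%).

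The direction of any bias is open and its size cannot be derived from the protocol. Under the assumed values above, the observed rate ratio with no true effect ranges from 0.88 to 1.14. It is 1.00 if both arms miss the same share.

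The conclusion rests on two assumptions: that fever is one of the prompts for culture in practice, and that knowing the arm can influence ordering. It does not show that the endpoint will be biased, nor that infection under cooling will be under-counted. It supports an inexpensive supplementary analysis, not a change of endpoint.

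**What to change.** In section 9.4, keep the all-culture endpoint and its test, and add:

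1. A supplementary comparison by arm of culture-proven infection limited to the scheduled post-randomization blood (days 1 to 3) and urine (days 2 and 4) cultures.
2. Beside it, the number of unscheduled cultures sent per child-day, by arm and source.
3. Respiratory and other infections shown separately by arm, with a note that the restricted comparison cannot address them.

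In sections 6.3 and 6.4, mark each recorded culture as scheduled or clinician-ordered.

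**Cost.** No extra sampling and no change to care, since all culture results are already recorded. The restricted comparison will have fewer events and a wider interval. The mark may need one extra data field, because the protocol mentions none that separates a routine culture from an additional one sent on the same day.

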8.3 Intervention Period (0 to 120 Hours)

Study interventions will begin after randomization. During the intervention period, vital signs will be monitored for all patients. Safety laboratories to measure serum chemistry, coagulation parameters, and hematologic parameters will also be collected. Information on daily chest x-rays will also be collected. Chest x-rays are performed routinely on patients after cardiac arrest to assess for signs of new infiltrates and to determine proper positioning of tubes including the esophageal temperature probe. The results of all blood, urine and respiratory cultures during the intervention period will be recorded. Adverse events, concomitant medications, and procedures and therapies administered will be recorded for both groups.

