11.2.3 Data Collection Procedures for Adverse Events

After patient randomization, all adverse events (including serious adverse events), whether anticipated or unanticipated, will be recorded according to the date of first occurrence, severity, and their duration, as well as any treatment prescribed. Any medical condition present at the time of randomization, recorded in the patient's baseline history at study entry, which remains unchanged or improves, will not be recorded as an adverse event at subsequent evaluations. However, worsening of a medical condition that was present at the time of randomization will be considered a new adverse event and reported.

Abnormal laboratory values that are clinically significant will be recorded as adverse events and the clinical site investigator will assess the severity and relationship to the study. Laboratory values that are abnormal at the time of randomization and that do not worsen will not be recorded as adverse events.

Adverse events will be coded using the MedDRA coding vocabulary. Coding will be done centrally at the DCC because this requires specific training.

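### As written, the infection safety endpoint takes in cultures drawn before study treatment, and the 7-day safety windows have conflicting starts and ends

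*Protocol*

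**What the plan says.** **Endpoint definition.** Protocol 4.4 lists "Incidence of culture proven infection (blood, urine, respiratory, or other) within 7 days of cardiac arrest"; 1.2.4 and 9.4 define it the same way. Arrhythmias and blood products also carry a 7-day window from arrest in these sections.

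**Monitoring.** Protocol 6.4 says infection events are assessed by examining "all cultures (blood, urine, and respiratory) obtained from the time of randomization through Day 7 (168 hours". It records arrhythmias and blood products from randomisation through Day 7.

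**Culture schedule and recording.** Protocol 6.3 states: "Blood cultures will be obtained at the time of randomization and on days 1, 2, and 3". For urine: "Urine cultures will be obtained at the time of randomization and on days 2 and 4". No respiratory culture is scheduled at randomisation. The same section adds: "The final results of all cultures sent within 7 days of enrollment will be obtained and recorded in the database". It defines days as midnight-to-midnight periods and Day 1 as the first full one after randomisation.

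**Data collection.** Protocol 8.4 records "cultures conducted up to seven days after cardiac arrest" and blood products within seven days of the arrest. Protocol 8.2 collects infection status at baseline. Protocol 8.3 states: "Study interventions will begin after randomization".

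**The concern.** A culture taken at randomisation shows what the child carried before study cooling or controlled normothermia. If its positive result counts as an infection event, the endpoint mixes prevalent with new infection. Baseline infection status is collected, but no endpoint definition uses it.

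The conflicting windows add to this. An arrest origin, read literally, admits events before randomisation. The clearest case is blood products given during resuscitation, because 8.4 has them recorded from the arrest.

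Infection is a named safety endpoint. Section 2.2.2 mentions a trend toward more infection in one adult trial, and 2.3.3 lists infection among the potential adverse effects. In a harm comparison, a pull toward no difference is the unsafe direction. Section 2.3.2 describes in-hospital children as commonly having major pre-existing or acute illness, so some baseline positivity is plausible there, although the protocol does not quantify it.

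**Working it through.** **1. Are the randomisation cultures inside the event rule?** Section 6.3 schedules blood and urine cultures at randomisation. Section 6.4 draws on all cultures from that same time. Section 8.3 puts the intervention after randomisation. A positive randomisation culture is therefore before treatment and, on the plain wording, inside the rule. No other section takes it out.

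**2. The windows side by side**

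| Item | From arrest | From randomisation | From enrolment |
|---|---|---|---|
| Infection | 1.2.4, 4.4, 8.4, 9.4 | 6.4 | 6.3 |
| Arrhythmias | 1.2.4, 4.4, 9.4 | 6.4 | none |
| Blood products | 1.2.4, 4.4, 8.4, 9.4 | 6.4 | none |

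- *Start.* Section 6.1 requires randomisation within six hours of ROSC/ROC. The two main origins thus differ by at most 6 hours plus time in arrest; 6/168 = 3.6% of the window.
- *End, in hours after randomisation.* Seven days from arrest ends at about 168 - 6 = 162 to 168 (slightly earlier once time in arrest is counted). The parenthesis in 6.4 gives 168. Calendar Day 7 under 6.3 ends at 168 plus the 0 to 24 hours to the first midnight, so 168 to 192. The spread is about 192 - 162 = 30 hours.

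**3. Effect on the comparison (illustration only).** The protocol states no infection rate, baseline-positive rate or power for this endpoint, so there is no figure to reproduce.

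Assumptions: new infection r0 = 30% and r1 = 40%; a share b of each arm is baseline-positive, with b = 5% or 20%. From the protocol: two-sided alpha 0.05 (9.1), 1:1 allocation (6.1), and n = 450/2 = 225 per arm, the low end of in-hospital enrolment (9.6).

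- Counted as events: p = b + (1 - b)r.
- Excluded: p = r, with n(1 - b) per arm.
- Kept as non-events: p = (1 - b)r, with n per arm.

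Power = Φ{[|p1 - p0| - 1.96√(2p̄(1 - p̄)/n)] / √[(p0(1 - p0) + p1(1 - p1))/n]}, where p̄ is the mean of p0 and p1.

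Example, b = 20%, counted: p0 = 0.20 + 0.80 × 0.30 = 0.44; p1 = 0.20 + 0.80 × 0.40 = 0.52. Power = Φ[(0.08 - 1.96 × 0.0471)/0.0470] = Φ(-0.26) = 40%.

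| b | Handling | Risks | n per arm | Rate ratio | Power |
|---|---|---|---|---|---|
| 0 | none needed | 30.0% v 40.0% | 225 | 1.33 | 60% |
| 5% | counted | 33.5% v 43.0% | 225 | 1.28 | 55% |
| 5% | excluded | 30.0% v 40.0% | 213.75 | 1.33 | 58% |
| 5% | non-events | 28.5% v 38.0% | 225 | 1.33 | 57% |
| 20% | counted | 44.0% v 52.0% | 225 | 1.18 | 40% |
| 20% | excluded | 30.0% v 40.0% | 180 | 1.33 | 51% |
| 20% | non-events | 24.0% v 32.0% | 225 | 1.33 | 47% |

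On unrounded values, counting baseline positives costs about 3 to 4 points of power at b = 5% and about 8 to 12 points at b = 20%, against the two alternatives.

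**The case against.** The best defence is that 6.4 is a monitoring section that names a data source and not a case definition. The word incidence in 4.4 ordinarily means new cases, and a randomisation culture with a baseline infection status is how a trial separates old from new. An analysis plan, not at hand, may combine them. This partly stands: inclusion is the plain reading, not the only one. But such a plan would have to narrow the wording of 6.4, and it would inherit three different window origins.

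Four stronger readings are tempting and not supported:

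- *That 11.2.3 contradicts the endpoint.* Its rule that a condition "which remains unchanged or improves, will not be recorded as an adverse event" governs adverse events, not safety endpoints. It also provides a separate channel: 11.2.4 puts culture-positive infection on the expedited list, and under 11.2.5 the DSMB reviews all adverse events.
- *That the arrest rhythm would count as an arrhythmia event.* The endpoint wording alone would allow it, but 6.4 records arrhythmias only from randomisation.
- *That 20 points of power are lost at 20% baseline-positive (60% to 40%).* The 60% comparator assumes that baseline-positive children acquire new infections at the full rate. Against excluding them or keeping them as non-events, the loss is about 8 to 12 points.
- *That other cultures go uncollected.* The first bullet of 6.4 omits this category, but the second records all cultures without limiting the type. The lists need alignment; data are not shown to be lost.

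**Conclusion.** The point holds as a defect of definition. Applied as written, the rules admit infections present before treatment. The 7-day windows have three stated origins, and their ends can differ by about 30 hours. The start gap itself is small, about six hours plus time in arrest; its clearest consequence is that resuscitation blood products could enter.

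The direction of the effect is toward a rate ratio of 1. It is non-differential by expectation and favours neither arm by design. A reader might infer that a real harm of cooling will be hidden. The documents do not support that: they give no baseline-positive rate, 10.4.2 says only that infection rates should be high in both groups, and no power is claimed for this endpoint. The power figures rest wholly on the assumed 30% v 40% and 5% to 20%. Severity is minor to moderate.

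**What to change.** - Use randomisation as the single origin, with one stated end, for every 7-day safety endpoint in 1.2.4, 4.4, 6.3, 6.4, 8.4 and 9.4. State whether the end is 168 hours or calendar Day 7.
- Use one list of culture types in 4.4, 6.4 and 9.4.
- Count as an infection event only (a) a positive culture drawn after the randomisation culture that is new relative to that culture and to the baseline infection status in 8.2, or (b) a documented worsening of a baseline infection, in line with the treatment of worsening in 11.2.3. The 8.2 status is the only baseline source for respiratory infection, so its recording must be specific enough to serve.
- Report baseline-positive children separately by arm.

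The cost is wording in six sections and slightly more derivation work. Cultures and baseline infection status are already collected, and clinical care does not change. Stated infection rates will be lower.
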